8.4 Detection of Bias

Placebo subjects might drop out earlier than romiplostim subjects and we would detect this in our summary of disposition and IP exposure tables. Sensitivity analyses for the primary analysis specified in [Section 9.5.1](#) address the potential of early drop out or discontinuation.

8.5 Outliers

Any suspected outliers will be investigated by the study team and will be included in the database unless determined to be an error or there is supporting evidence or explanation to justify the exclusion. Any outliers excluded from the analysis will be discussed in the Clinical Study Report (CSR), including the reasons for exclusion and the impact of their exclusion on the study

Pharmacokinetic (PK) [plasma] concentration data will be evaluated for outliers by visual inspection, and decisions to re-assay individual samples will be made in accordance with standard pharmacokinetic evaluation practice.

8.6 Distributional Characteristics

The statistical assumptions for analysis methods will be assessed. If the assumptions for the distributional characteristics are not met, these will be described and further analyses may be carried out using data transformations or alternative analysis methods. The use of transformations or alternative analysis methods will be justified in the final study report.

8.7 Validation of Statistical Analyses

Programs will be developed and maintained, and output will be verified in accordance with current risk-based quality control procedures.

Tables, figures, and listings will be produced with validated standard macro programs where standard macros can produce the specified outputs.

The production environment for statistical analyses consists of Amgen-supported versions of statistical analysis software; for example, the SAS System version 9.4 or later or using R.

9. Statistical Methods of Analysis

9.1 General Considerations

Continuous variables will be summarized descriptively by the n, mean, standard deviation, median, Q1 (25th percentile), Q3 (75th percentile), minimum, and maximum. The confidence interval and standard error for the mean will also be summarized for efficacy variables that are continuous. Categorical variables will be summarized descriptively by the number and percentage in each category. Missing values will be shown as a separate category. The confidence interval will also be summarized for dichotomous efficacy variables.

Time to event variables will be summarized with hazard ratios, Kaplan-Meier curves, Kaplan-Meier quartiles, the number of subjects at risk, the number of subjects censored, and the number of subjects with events.

Where confidence intervals are provided, these will be 2-sided at the 95% level, unless otherwise specified.

The primary efficacy endpoint will be compared between the romiplostim and placebo groups at the significance level of 0.05 using a 2-sided test. If statistical significance is achieved for the primary endpoint in favor of romiplostim, **the following secondary efficacy endpoints will be tested using a fixed sequence hierarchical testing procedure to control the family-wise Type I error rate below 2-sided 0.05 level. The family of hypotheses is ordered as follows:**

- the depth of platelet count nadir from the start of the first on-study chemotherapy cycle through the end of the treatment period
- the time to first platelet response, defined by platelet count $\geq 100 \times 10^9/L$, in the absence of platelet transfusions during the preceding 7 days.
- the duration-adjusted event rate of \geq grade 2 bleeding events as assessed per CTCAE version 5.0 grading scale
- overall survival
- platelet transfusion(s) during the treatment period
- achieving platelet count $\geq 100 \times 10^9/L$ at any time after study day 1 to week 4 (ie, 7 days after the planned third dose of investigational product) in the absence of platelet transfusions during the preceding 7 days

Starting with the hypothesis of platelet count nadir, if any null hypothesis in the sequence is rejected at a 2-sided significance level of 0.05, then the subsequent hypothesis will be tested; if any null hypothesis is accepted, then the subsequent hypotheses will not be tested.

Summary statistics without formal testing will be provided for other endpoints.

9.2 Subject Accountability

The number and percent of subjects who were randomized, received investigational product, completed investigational product, discontinued investigational product and reasons for discontinuing, completed study, discontinued study and reasons for discontinuing will be summarized by treatment group. The number of subjects screened will also be reported.

The number and percentage of subjects randomized will be tabulated by the stratification factor and also by country and study site within country. Key study dates for the first subject randomized, last subject randomized, and data cut-off date for analysis will be presented.

The number and percentage of subjects included in each analysis set (described in [Section 6](#)) will be presented.

Follow-up time (time from study day 1 to EOS or last contact date) will be summarized by treatment group at each analysis using descriptive statistic.

9.3 Important Protocol Deviations

Important Protocol Deviations (IPDs) categories are defined by the study team before the first subject's initial visit and updated during the IPD reviews throughout the study prior to database lock. These definitions of IPD categories, subcategory codes, and descriptions will be used during the course of the study. Eligibility deviations are defined in the protocol. IPDs due to COVID-19 will be summarized separately.

9.4 Demographic and Baseline Characteristics

The following demographics and baseline characteristics will be summarized by treatment group and overall using descriptive statistics for the FAS.

- The stratification factor of tumor type (gastrointestinal, **pancreatic**, colorectal)
- The stratification factor of baseline platelet count ($< 50 \times 10^9/L$, $\geq 50 \times 10^9/L$)
- Age (continuous and categorized ≤ 65 years, > 65 years)
- Sex (Male, Female)
- Race (White, Black or African American, Asian, American Indian or Alaska Native, Native Hawaiian or Other Pacific Islander, Other)
- Ethnicity (Hispanic or Latino, Not Hispanic or Latino)
- Region (United States, Europe, Rest of World)
- Body mass index
- Weight
- Height
- ECOG (0-1, ≥ 2)
- Stage of disease (Stage 3, Stage 4 or recurrent disease)
- Line of chemotherapy treatment (< 2 , ≥ 2)
- **Type of chemotherapy regimen (FOLFOX, FOLFIRINOX, FOLFOXIRI, CAPEOX)**
- Number of previous chemotherapy cycles (≤ 2 , > 2)
- Dose of previous chemotherapy cycle before entering the study (Modified dose, Full dose)
- Prior or Concurrent Bevacizumab use (Yes, No)
- Baseline platelet count (continuous and categorized by CTCAE version 5.0 thrombocytopenia grade)
- Prior bleeding events (Yes, No)

- Prior platelet transfusions (Yes, No)
- Prior use of erythropoiesis-stimulating agent (Yes, No)
- Prior use of granulocyte colony-stimulating factor (Yes, No)
- Prior use of programmed cell death 1 inhibitors or programmed cell death ligand 1 inhibitors (Yes, No)
- Concurrent use of programmed cell death 1 inhibitors or programmed cell death ligand 1 inhibitors (Yes, No)

9.5 Efficacy Analyses

The efficacy analyses below will be conducted.

9.5.1 Analyses of Primary Efficacy Endpoint(s)

The primary endpoint is the proportion of subjects with no thrombocytopenia induced dose modification. **The primary analysis will be based on the adjudication committee (AC) assessment of thrombocytopenia-induced dose modification. The proportion along with a 95% CI will be provided for each treatment group.** A 2-sided CMH test will be used to compare groups controlling for the stratification factors of tumor type and baseline platelet count. The Mantel-Haenszel estimate of common odds ratio for romiplostim vs placebo will be estimated along with a 95% CI for each treatment group and the difference in proportions between treatment groups will be provided with a 95% CI.

For primary analysis, subjects with missing observations for cycle 2 and/or cycle 3, or who discontinued any myelosuppressive agent early, are considered as not meeting the criteria of the primary endpoint. The following sensitivity analyses will be explored:

A sensitivity analysis using the investigator's assessment on thrombocytopenia -induced dose modification will be performed. The number and percentage of subjects with concordant and discordant assessments per investigator and AC will be summarized.

If more than 10% of subjects in the full analysis set have COVID-19 related IPDs with missing chemotherapy without platelet count assessment for cycle 2 or cycle 3, a sensitivity analyses may be explored by excluding those subjects with COVID-19 related IPDs.

For each specified covariate in [Section 4.1](#), sensitivity analyses will be conducted to evaluate any potential confounding: (1) a 2-sided CMH test checking conditional independence between treatment groups and primary endpoint outcomes controlling for each individual covariate, (2) a logistic regression with primary endpoint outcome as the dependent variable and explanatory variables from treatment group, the specified covariate, and interaction of treatment by covariate.

Subgroup exploratory analyses will also be performed to explore the consistency of the treatment effect between subgroups described in [Section 4.2](#). FAS will be used for the primary endpoint analysis.

9.5.2 Analyses of Secondary Efficacy Endpoint(s)**9.5.2.1 Depth of Platelet Count Nadir From the Start of the First On-study Chemotherapy Cycle Through the EOTP (1)**

The depth of platelet count nadir after the start of the 1st on-study chemotherapy cycle through the EOTP will be summarized and compared between romiplostim and placebo group. Summary statistics will include n, mean, standard deviation, standard error, median, Q1, Q3, minimum, and maximum. Linear regression models will be used to compare the mean nadir between the romiplostim and placebo groups. Dependent variables will include the treatment group, the stratification factors of tumor type and baseline platelet count, and the interactions between treatment group and the stratification factor. FAS will be used for the all the secondary endpoint analyses.

The following sensitivity analyses will be explored for the endpoint if subjects never started the first on-study chemotherapy cycle or never have platelet count measured after the first on-study chemotherapy cycle:

- (1)** Impute platelet nadir using the lowest nadir value for the remaining subjects in the treatment group
- (2)** Impute platelet nadir using the lowest platelet count from baseline to the last platelet count assessment
- (3)** Impute platelet nadir using the mean nadir value for the treatment group
- (4)** Sensitivity analysis excluding the missing subjects

The normality assumption for linear regression models will be checked using a normal probability plot of the residuals and the Shapiro-Wilk (SK) test ([Shapiro and Wilk 1965](#)).

The following steps will then take place:

If the normal probability plot and the SK test show strong evidence against the normality assumption, log-transformation will be conducted. After the transformation, the normality will be checked again using the normal probability plot of the residuals and the SK test:

- a. If the normality assumption holds after the log-transformation, linear regression models will be used on log-transformed variables to compare the mean nadir.
- b. If the normality assumption does not hold after the log-transformation, the nonparametric van Elteren test will be used to compare the mean nadir.

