applicable. Delayed, reduced, omitted, and discontinued doses within a cycle will also be counted as dose modifications even if they do not cause the start of the next cycle to be delayed. Note: For subjects who discontinue investigational product prior to completing 3 cycles of chemotherapy, chemotherapy dose and schedule should be recorded through 3 on-study chemotherapy cycles to the end of the third on-study cycle. In this situation the local laboratory assessments recorded must be those taken prior to scheduled chemotherapy visits and used to inform decisions relating to chemotherapy dose modification. **Any local laboratory tests performed in the cycle prior to enrollment should be recorded if they are used to determine chemotherapy dose in study cycle 1. Any local laboratory tests performed outside of the study visits should be recorded if they are used to determine chemotherapy dose in study cycles 1, 2, and 3 (see Schedule of Activities [Section 2.2] for further information).**

For the primary endpoint, we will capture information at each weekly study visit on the actual chemotherapy dose and unit, start/stop dates, whether the subject experienced a dose reduction, delay, or omission due to thrombocytopenia with platelet counts below  $100 \times 10^9/L$ , whether the subject experienced chemotherapy treatment discontinuation due to thrombocytopenia with platelet counts below  $100 \times 10^9/L$  or per the guidelines provided when there is thrombocytopenia for the specific tumor types and regimens (Section 7.4.1.2), and whether there was a reason other than thrombocytopenia for dose reduction, delay, omission, or discontinuation. Chemotherapy dose delays, dose reductions, and dose omissions will be permitted according to chemotherapy dose modification guidelines outlined in Section 7.4.1.2. For each planned chemotherapy agent, any thrombocytopenia related modifications which include dose reduction, dose delays, dose omission, and treatment discontinuation, at any time during on-study cycle 2 or 3 will be counted as failure in the primary endpoint analysis. An independent adjudicator will periodically verify the reason for chemotherapy dose modifications during on-study cycles 1-3.

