Duration-Adjusted Event Rate for AE during the Follow-up Period

The duration-adjusted AE incidence rate within a treatment group is expressed as the number of events per 100 subject-years from the 31 days after the date of last dose of investigational product to EOS:

$$\text{Duration-adjusted event rate} = \frac{\text{Total number of events}}{\text{Total duration in subject-years}} \times 100$$

Endpoints: Primary - No Thrombocytopenia-induced Modification of any Myelosuppressive Treatment Agent in the Second and Third Cycles

Subjects will meet the criteria of the primary endpoint if there is no thrombocytopenia-induced modification of any myelosuppressive treatment agent in the second and third cycles of the planned on-study chemotherapy regimen.

A thrombocytopenia-induced modification is defined as any dose reduction, dose delay, dose omission, and/or early chemotherapy treatment discontinuation due to low platelet counts less than $100 \times 10^9/\text{L}$.

For the purposes of determining dose reductions, the actual on-study chemotherapy doses will be compared to the planned chemotherapy dose recorded on study day 1, defined by the dose administered in the chemotherapy cycle immediately prior to study entry.

For the purposes of determining dose delays, the difference between the start date of a given chemotherapy cycle and the start date of the chemotherapy cycle immediately prior to the given cycle will be calculated and compared to the planned cycle length of the regimen.

Delayed, reduced, omitted, and discontinued doses within a cycle will also be counted as dose modifications even if they do not cause the start of the next cycle to be delayed. Note: For subjects who discontinue investigational product prior to completing 3 cycles of chemotherapy, chemotherapy dose and schedule should be recorded through 3 on-study chemotherapy cycles to the end of the third on-study cycle.

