An independent adjudicator will periodically verify the reason for chemotherapy dose reduction, dose delay, dose omission and treatment discontinuation during on-study cycles 1-3. For each planned chemotherapy agent, any dose delays, dose reduction, dose omission, and treatment discontinuation at any time during on-study cycle 2 or 3, where the adjudicated reason is thrombocytopenia, will be counted as failure in the primary endpoint analysis. Chemotherapy dose modification in the first cycle of the planned on study chemotherapy regimen will not be counted toward the primary endpoint even if due to CIT. If a chemotherapy dose modification occurs during on-study cycle 1 the new baseline for comparison will reset to the chemotherapy dose modifications that occurred in cycle 1. This will also apply to dose modifications occurring during on study cycle 2 that are not attributable to CIT.

Chemotherapy dose delays dose reductions, and dose omissions will be permitted according to chemotherapy dose modification outline in section 7.4.1.2 of the protocol.

Endpoints: Secondary (1) – Platelet Count Nadir from the Start of the First On-study Chemotherapy Cycle through the End of the Treatment Period

The platelet count nadir from the start of the first on-study chemotherapy cycle through the EOTP is defined as the lowest platelet count observed after the date of the earliest myelosuppressive chemotherapy agent delivered in the first on-study cycle through the EOTP day.

For subjects who never started the first on-study chemotherapy cycles or who never have platelet count measured after the first on-study chemotherapy cycle, the platelet count at baseline will be used for the endpoint.

Endpoints: Secondary (2) – Time to First Platelet Response

Time to first platelet response is defined as the number of days from study day 1 to the date of achieving a platelet count $\geq 100 \times 10^9/L$ **in the absence of platelet transfusions during the preceding 7 days**. It is calculated as:

Date of first platelet response – study day 1 + 1.

If a platelet transfusion occurred during the 7 days preceding a platelet count then that platelet count will not be considered a response event if it is $\geq 100 \times 10^9/L$. Subjects who did not achieve a response event during the treatment period are censored at their last platelet count assessment date up to EOTP or at **randomization date** if they did not have any **post-baseline** platelet assessments.

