8.3 Handling of Missing and Incomplete Data

For primary analysis **on the thrombocytopenia-induced dose modification**, subjects with **complete missing visits (missing chemotherapy and none of the protocol specified assessments are performed) or partial visits (missing chemotherapy but some of the protocol specified assessments are performed)** without platelet count assessment for cycle 2 and/or cycle 3 are imputed as **having thrombocytopenia-induced dose modification in cycle 2 and/or cycle 3**. **Partial missing visits with platelet count assessment will be recorded following the dose modification rule in protocol section 7.4.1.2. Subjects with missing chemotherapy but having platelet count assessment within two days of the planned chemotherapy start or chemotherapy discontinuation will be determined by the adjudication committee.**

Potential **complete or partial missing or visits** missing assessments may result from below reasons:

- Death
- Early discontinuation of chemotherapy
- Consent withdrawal or lost to follow up

The rules for handling partial dates are described in [Appendix B](#)

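### SAP 9.5.1 counts any early stop of a myelosuppressive agent as a primary-endpoint failure, with no condition on reason or cycle; for a confined group of subjects this conflicts with SAP 5, SAP 8.3 and the protocol

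*SAP*

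**What the plan says.** The endpoint definition in SAP Section 5 treats as a modification any "early chemotherapy treatment discontinuation due to low platelet counts less than" 100 × 10⁹/L, alongside reductions, delays and omissions. It then says that events in cycle 2 or 3, "where the adjudicated reason is thrombocytopenia, will be counted as failure in the primary endpoint analysis". Modifications in cycle 1 do not count. Protocol 9.2.2.3 fails "any thrombocytopenia related modifications which include dose reduction, dose delays, dose omission, and treatment discontinuation, at any time during on-study cycle 2 or 3", and protocol 10.3.2.2.1 defines the endpoint in the same way.

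For missing data, SAP 8.3 has three parts:
- Visits with no chemotherapy and "without platelet count assessment for cycle 2 and/or cycle 3 are imputed as" modified, whatever the cause.
- Cases of missing chemotherapy in subjects "having platelet count assessment within two days of the planned chemotherapy start or chemotherapy discontinuation will be determined by the adjudication committee".
- "Partial missing visits with platelet count assessment will be recorded following the dose modification rule in protocol section 7.4.1.2".

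Protocol 10.2.4 contains the first two parts but not the third.

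SAP 9.5.1 opens with "The primary analysis will be based on the adjudication committee (AC) assessment of thrombocytopenia-induced dose modification". Its next paragraph says that, for the primary analysis, subjects with missing observations for cycle 2 or 3, "or who discontinued any myelosuppressive agent early, are considered as not meeting the criteria of the primary endpoint".

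SAP 8.4 says that the sensitivity analyses in 9.5.1 address early drop-out or discontinuation. SAP 10 declares no change from the protocol.

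**The concern.** Take a subject who stops one agent in cycle 2 for a reason adjudicated as not thrombocytopenia, keeps attending, has platelet counts and receives the other agents as planned. Under SAP 5 and the protocol, that stop is not a failure. Under the sentence in 9.5.1 it is. Two programmers working from the same SAP could produce different primary-endpoint numerators.

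This endpoint is the first test in the fixed sequence (SAP 9.1), so all six secondary tests depend on it. It is also the endpoint of the interim futility analysis (SAP 7.1). If the wording still conflicts when the study is unblinded, the choice of rule is made with the results in view.

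**Working it through.** **Step 1. The rules side by side.**

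| Subject | SAP 5 / protocol 9.2.2.3 | SAP 8.3 / protocol 10.2.4 | SAP 9.5.1 |
|---|---|---|---|
| Stop in cycle 2 or 3, adjudicated as thrombocytopenia | Failure | Committee, if count within two days | Failure |
| Non-platelet stop in cycle 2 or 3, count within two days | Not a failure on that account | Committee | Failure |
| One agent stopped for a non-platelet reason; visits and other agents continue | Not a failure on that account | Not a missed visit | Failure |
| Agent stopped in cycle 1; other agents continue | Cycle 1 does not count; baseline resets | Not a missed visit | Failure |
| Cycle 2 or 3 visit with no chemotherapy and no count | Depends on reason | Failure, any cause | Failure |

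The conflict lies in rows 2 to 4. In row 5, 9.5.1 and the missing-visit rule agree; what is unstated there is whether a documented non-platelet reason overrides the imputation.

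**Step 2. The sensitivity analyses in 9.5.1.** They are: investigator instead of committee assessment; a conditional exclusion of subjects with COVID-19-related deviations; and covariate-by-covariate CMH and logistic models. None is stated to vary the early-discontinuation rule.

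**Step 3. Reproduce the plan's power.** Inputs from protocol 10.1 and SAP 3.2: 108 and 54 subjects, per-cycle success 60% and 30%, correlation 0.7, two-sided 0.05. The two-cycle rate is p² + 0.7p(1 − p).
- Romiplostim: 0.36 + 0.7 × 0.24 = 0.528
- Placebo: 0.09 + 0.7 × 0.21 = 0.237
- Odds ratio: (0.528/0.472)/(0.237/0.763) = 3.60, against a stated 3.6

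Unstratified log-odds-ratio power is Φ(ln OR/SE − 1.96), with SE² = 1/(108 × 0.528 × 0.472) + 1/(54 × 0.237 × 0.763) = 0.1396, so SE = 0.374. Then 1.281/0.374 − 1.96 = 1.47, and power is 92.9%, against a stated 93%. An exact single-stratum CMH calculation gives 93.4% with continuity correction and 95.5% without.

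**Step 4. Illustrate the 9.5.1 rule.** Assume that a share d of each arm stops for a non-platelet reason and would otherwise succeed at the arm's rate. The 9.5.1 rate is then p(1 − d), where p is the two-cycle rate from Step 3. All values of d are assumptions.

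| d romiplostim / placebo | Rates | OR | Power |
|---|---|---|---|
| 0 / 0 | 52.8% vs 23.7% | 3.60 | 92.9% |
| 5% / 5% | 50.2% vs 22.5% | 3.46 | 90.7% |
| 10% / 10% | 47.5% vs 21.3% | 3.34 | 88.1% |
| 15% / 15% | 44.9% vs 20.1% | 3.23 | 85.1% |
| 20% / 10% | 42.2% vs 21.3% | 2.70 | 73.1% |
| 10% / 20% | 47.5% vs 19.0% | 3.87 | 92.6% |

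The result depends on who the stoppers are. If half of them would otherwise succeed in both arms, 15% in each arm subtracts 7.5 points from each rate (45.3% vs 16.2%), giving OR 4.28 and power 93.7%. That assumption gives placebo stoppers about twice their arm's success rate.

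**Step 5. No true effect.** Suppose 52.8% in both arms are free of thrombocytopenia-induced modification, with non-platelet stops of 30% on placebo and 10% on romiplostim. The 9.5.1 rates are 0.528 × 0.7 = 37.0% and 0.528 × 0.9 = 47.5%, an apparent OR of 1.54. The test rejects in 19% of trials with continuity correction and 25% without.

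**The case against.** The best defence is that the sentence in 9.5.1 is shorthand for SAP 8.3. Both deal with missing cycle 2 and 3 data, 8.3 lists early chemotherapy discontinuation as a cause of missing visits, and early discontinuation is also SAP 5's own term inside its platelet-based definition. That may well explain the missing-observations clause. It does not settle the second clause, a separate alternative that needs neither a missed visit nor a missing count. The sponsor may have meant the narrow reading, but the text does not say so.

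A second defence is that failing all early stops is a conservative composite in keeping with an objective of on-time, full-dose chemotherapy. It is a reasonable quantity to show, but it is not the protocol's definition, and Steps 4 and 5 show that it is not reliably conservative.

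Three stronger readings are tempting, and the documents do not support them:
- That the protocol and the rest of the SAP fail only thrombocytopenia-induced stops. The missing-visit rule fails some stops whatever the cause.
- That no sensitivity analysis varies the rule. The 9.5.1 sentence is framed for the primary analysis, and the text does not say whether it carries over to the investigator-assessed analysis. It can be said only that none is stated to vary it. SAP 8.4 is itself general and mainly about earlier drop-out on placebo.
- That 9.5.1 contradicts its own opening on committee assessment. A committee-based endpoint with an added rule for stopped subjects is ordinary layering. The conflict is with SAP 5, SAP 8.3 and the protocol.

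**Conclusion.** The conflict is real and concerns the primary endpoint. As written, 9.5.1 gives a different numerator from SAP 5 and the protocol for three groups: subjects who stop an agent for a non-platelet reason and have a platelet count; subjects who stop one agent while visits and other agents continue; and stops outside cycles 2 and 3. SAP 10 does not declare the departure. It should be resolved before unblinding.

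Its numerical size is unknown. A reader might infer from Step 4 that the trial loses a set amount of power, or from Step 5 that the rule favours romiplostim. Neither follows, because the documents give no rate of non-platelet stops and no indication that such stops differ by arm. The fall to between 91% and 85% assumes 5% to 15% stops in each arm, success otherwise at the arm's rate, and that every such stop is classified differently by the two rules. Stops with a missed visit and no count fail under both, so the affected share would be smaller than the total stop rate.

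**What to change.** Before unblinding, replace the 9.5.1 sentence with one ordered rule limited to cycles 2 and 3:

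1. A discontinuation of an agent in cycle 2 or 3 is a failure when the blinded adjudicated reason is thrombocytopenia. A stop adjudicated as non-platelet is not a failure on that account.
2. Missing cycle 2 or 3 chemotherapy with a platelet count within two days of the planned start or the discontinuation is decided by the committee.
3. A cycle 2 or 3 visit with neither chemotherapy nor a platelet count is imputed as a failure, as protocol 10.2.4 already provides. Where this step and step 1 could both apply, this step governs, including for a stop with a documented non-platelet reason but no count.

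Align the extra sentence in SAP 8.3 on partial visits, which protocol 10.2.4 lacks, with this order. State that it applies only where the committee rule does not, without widening the two-day window.

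Keep the rule that any early discontinuation or missing cycle 2 or 3 is a failure as a named sensitivity analysis. That makes the statement in SAP 8.4 good and shows how much depends on counting non-platelet stoppers as successes.

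The cost is SAP wording in 9.5.1 and 8.3 and one extra table. No new data are needed: protocol 7.4.1.2 and 9.2.2.3 already require the reasons for discontinuation to be recorded and independently verified.
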